Grade 4 (ANC < $0.5 \times 10^9/L$)	Omit dose until resolved to \leq Grade 2, then: If resolved in ≤ 7 days, then maintain dose level If resolved in > 7 days, then $\downarrow 1$ dose level
Febrile neutropenia (ANC < $1.0 \times 10^9/L$, with a single temperature of $\geq 38.3^\circ C$ or a sustained temperature of $\geq 38^\circ C$ for more than one hour)	Omit dose until clinically resolved and neutropenia \leq Grade 2, then $\downarrow 1$ dose level

Worst toxicity (CTCAE 4.03 Grade)*	Dose Modifications for ceritinib
Thrombocytopenia	
Grade 1 (PLT < LLN - $75 \times 10^9/L$)	Maintain dose level
Grade 2 (PLT <75 and $\geq 50 \times 10^9/L$)	
Grade 3 (PLT <50 and $\geq 25 \times 10^9/L$)	Omit dose until resolved to \leq Grade 2, then: If resolved in ≤ 7 days, then maintain dose level If resolved in >7 days, then \downarrow 1 dose level
Grade 4 (PLT < $25 \times 10^9/L$)	Omit dose until resolved to \leq Grade 2, then \downarrow 1 dose level
HEPATIC	
Alkaline phosphatase and/or Gamma-glutamyl transpeptidase (GGT)	
Isolated elevations of any grade	Maintain dose level
Total Bilirubin** (for patients with Gilbert Syndrome these dose modifications apply to changes in direct [conjugated] bilirubin only)	
Grade 1 ($>$ ULN and $\leq 1.5 \times$ ULN)	Maintain dose level with liver function test (LFTs)*** monitored as per protocol
Grade 2 (>1.5 and $\leq 3.0 \times$ ULN) with AST or ALT $\leq 3.0 \times$ ULN	Omit dose until resolved to \leq Grade 1, then: If resolved in ≤ 7 days, then maintain dose level If resolved in >7 days, then \downarrow 1 dose level
Grade 3 (>3.0 and $\leq 10.0 \times$ ULN) with AST or ALT $\leq 3.0 \times$ ULN	Omit dose until resolved to \leq Grade 1, then: If resolved in ≤ 7 days, \downarrow 1 dose level If resolved in >7 days discontinue patient from ceritinib
Grade 4 ($>10.0 \times$ ULN)	Permanently discontinue patient from ceritinib
AST or ALT	
Grade 1 ($>$ ULN and $\leq 3.0 \times$ ULN)	Maintain dose level with LFTs*** monitored per protocol
Grade 2 (>3.0 and $\leq 5.0 \times$ ULN) without total bilirubin elevation to $>2.0 \times$ ULN	Maintain dose level with LFTs*** monitored per protocol
Grade 3 (>5.0 and $\leq 20.0 \times$ ULN) without total bilirubin elevation to $>2.0 \times$ ULN	Omit dose until resolved to \leq Grade 1 (or to baseline), then \downarrow 1 dose level

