Grade 4 ($>20.0 \times$ ULN) without total bilirubin elevation to $>2.0 \times$ ULN	Omit dose until resolved to \leq Grade 1 (or to baseline), then \downarrow 1 dose level
AST or ALT and concurrent Total bilirubin	
AST or ALT $>3.0 \times$ ULN and total bilirubin $>2.0 \times$ ULN in the absence of cholestasis or hemolysis	Permanently discontinue patient from ceritinib (Refer to Section 6.3.4.2 for additional follow-up)
PANCREATIC	
Amylase and/or lipase elevations (in the absence of clinical symptoms)	
Grade 1 ($>$ ULN and $\leq 1.5 \times$ ULN)	Maintain dose level
Grade 2 (>1.5 - $2.0 \times$ ULN)	Maintain dose level
Grade ≥ 3 ($> 2.0 \times$ ULN)	Omit dose until resolved to \leq Grade 1, then \downarrow 1 dose level
Note: Withhold ceritinib for acute onset of new or progressive unexplained abdominal symptoms, such as severe pain or vomiting; perform diagnostic procedures (e.g., abdominal CT scan or ultrasound) to exclude pancreatic pathology.	
RENAL	
Serum creatinine	
Grade 1 (>1 and $\leq 1.5 \times$ baseline; $>$ ULN and $\leq 1.5 \times$ ULN)	Maintain dose level
Grade 2 (>1.5 and $\leq 3.0 \times$ baseline; >1.5 and $\leq 3.0 \times$ ULN)	Omit dose until resolved to \leq Grade 1, then: If resolved in ≤ 7 days, then maintain dose level If resolved in >7 days, then \downarrow 1 dose level
Grade 3 ($>3.0 \times$ baseline; >3.0 and $\leq 6.0 \times$ ULN)	Omit dose until resolved to \leq Grade 1, then \downarrow 1 dose level
Grade 4 ($>6.0 \times$ ULN)	Permanently discontinue patient from ceritinib

Worst toxicity (CTCAE 4.03 Grade)*	Dose Modifications for ceritinib
Grade 1 (> ULN and <1.5 x ULN)	Maintain dose level
Grade 2 (≥1.5 and ≤3.0 x ULN)	Omit dose until resolved to ≤ Grade 1, then: If resolved in ≤7 days, then maintain dose level If resolved in >7 days, then ↓ 1 dose level
Grade 3 (>3.0 and ≤6.0 x ULN)	Omit dose until resolved to ≤ Grade 1, then ↓ 1 dose level
Grade 4 (>6.0 x ULN)	Permanently discontinue patient from ceritinib
GASTROINTESTINAL	
Diarrhea****	
Grade 1	Maintain dose level but adjust anti-diarrhea treatment
Grade 2 (despite maximal anti-diarrheal medication)	Omit dose until resolved to ≤ Grade 1, then maintain dose level. If diarrhea returns as ≥ Grade 2, then omit dose until resolved to ≤ Grade 1, then ↓ 1 dose level
Grade 3 (despite maximal anti-diarrheal medication)	Omit dose until resolved to ≤ Grade 1, then ↓ 1 dose level

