
* Common Terminology Criteria for Adverse Events (CTCAE) version 4.03. All dose modifications should be based on the worst preceding toxicity.
 
** If Grade 3 or 4 hyperbilirubinemia is due to the indirect (non-conjugated) component only, and hemolysis as the etiology has been ruled out as per institutional guidelines (e.g., review of peripheral blood smear and haptoglobin determination), then \downarrow 1 dose level and continue treatment at the discretion of the Investigator.
 
***LFTs include albumin, ALT, AST, total bilirubin, alkaline phosphatase and GGT
 
**** Dose modifications apply to patients who experience diarrhea despite appropriate antidiarrheal medication. This medication should be started at the first sign of abdominal cramping, loose stools or overt diarrhea (see Section 6.3.4.5)
 
***** Dose modifications apply to patients who experience nausea and/or vomiting despite appropriate antiemetic medication. This medication should be started at the first sign of nausea and/or vomiting (see Section 6.3.4.6)
	

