6.3.4.2 Guidelines for the follow-up of laboratory liver abnormalities

In patients with any clinically relevant laboratory liver abnormality, as defined below, hepatic toxicity monitoring must include **ALL** of the following liver function tests (LFTs): albumin, ALT, AST, total bilirubin (fractionated if total bilirubin $> 2.0 \times$ ULN), alkaline phosphatase and GGT. Note: for patients with Gilbert Syndrome, total and direct bilirubin must be monitored, but intensified monitoring applies to changes in direct bilirubin only.

In case of any occurrence of ALT/AST/total bilirubin increase to grade 2 the LFTs must be monitored weekly (or more frequently if clinically indicated) until the event resolves to \leq grade 1. Thereafter monitoring must be continued every other week (or more frequently if clinically indicated) for two additional cycles (e.g., 8 weeks). If there is no recurrence of grade 2 ALT/AST/total bilirubin elevations during this period, subsequent monitoring must be performed every 4 weeks. For patient with liver metastasis and grade 2 AST/ALT at baseline, increased monitoring is required for grade 3/4 AST/ALT; follow guidelines for grade 3 or 4 AST/ALT.

In case of any occurrence of ALT/AST/bilirubin increase to grade 3 or 4, LFTs must be monitored weekly (or more frequently if clinically indicated) until the event resolves to \leq grade 1 (or to baseline). Thereafter monitoring must be continued every other week (or more frequently if clinically indicated) for 4 additional cycles (e.g., 16 weeks). If there is no recurrence of \geq grade 2 ALT/AST/total bilirubin elevations during this period, subsequent monitoring must be performed every 4 weeks.

Patients who discontinue ceritinib treatment due to liver toxicity must be monitored weekly (or more frequently if clinically indicated) until the event resolves to \leq grade 1 or stabilization occurs (no CTCAE grade change over 4 weeks).

Patients with transaminase increase combined with total bilirubin (TBIL) increase may be indicative of potential DILI, and should be considered as clinically important events.

The threshold for potential DILI may depend on the patient's baseline AST/ALT and TBIL value; patients meeting any of the following criteria will require further follow-up as outlined below:

- For patients with normal ALT and AST and TBIL value at baseline: AST or ALT $> 3.0 \times$ ULN combined with TBIL $> 2.0 \times$ ULN

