- For patients with elevated AST or ALT or TBIL value at baseline: [AST or ALT $> 2 \times$ baseline AND $> 3.0 \times$ ULN] OR [AST or ALT $> 8.0 \times$ ULN], combined with [TBIL $> 2 \times$ baseline AND $> 2.0 \times$ ULN]

Medical review needs to ensure that liver test elevations are not caused by cholestasis, defined as: ALP elevation $> 2.0 \times$ ULN with R value (ALT/ALP in \times ULN) < 2 in patients without bone metastasis, or elevation of ALP liver fraction in patients with bone metastasis.

Note: (The R value is calculated by dividing the ALT by the ALP, using multiples of the ULN for both values. It denotes the relative pattern of ALT and/or ALP elevation is due to cholestatic or hepatocellular liver injury).

In the absence of cholestasis, these patients should be immediately discontinued from study drug treatment, and repeat LFT testing as soon as possible, preferably within 48 hours from the awareness of the abnormal results. The evaluation should include laboratory tests, detailed history, physical assessment and the possibility of liver metastasis or new liver lesions, obstructions/compressions, etc.

- Laboratory tests should include ALT, AST, albumin, creatine kinase, total bilirubin, direct and indirect bilirubin, GGT, prothrombin time (PT)/INR and alkaline phosphatase.
- A detailed history, including relevant information, such as review of ethanol, concomitant medications, herbal remedies, supplement consumption, history of any pre-existing liver conditions or risk factors, should be collected.
- Further testing for acute hepatitis A, B, C or E infection and liver imaging (eg, biliary tract) may be warranted.
- Obtain PK sample, as close as possible to last dose of study drug, if PK analysis is performed in the study.
- Additional testing for other hepatotropic viral infection (CMV, EBV or HSV), autoimmune hepatitis or liver biopsy may be considered as clinically indicated or after consultation with specialist/hepatologist.

All cases confirmed on repeat testing meeting the laboratory criteria defined above, with no other alternative cause for LFT abnormalities identified should be considered as "medically significant", thus, met the definition of SAE ([Section 8.3.1](#)) and reported as SAE using the term "potential drug-induced liver injury". All events should be followed up with the outcome clearly documented.

Refer to [Table 6-4](#).

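### Table 6-3 keeps the dose unchanged at total bilirubin >1.5–2.0 × ULN when AST and ALT are both >3.0–5.0 × ULN, although the same bilirubin triggers a hold with lower and with higher enzymes

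*Protocol*

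**What the plan says.** The hepatic part of Table 6-3 (Protocol Section 6.3.3) has three blocks that bear on this point.

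- **Total bilirubin, Grade 2.** The row reads "Grade 2 (>1.5 and $\leq 3.0 \times$ ULN) with AST or ALT $\leq 3.0 \times$ ULN". Drug is omitted until bilirubin is back to Grade 1 or below. It then resumes at the same dose if that took 7 days or less, and one level lower if it took longer. In Gilbert syndrome this block refers to direct bilirubin only.
- **AST or ALT.** The Grade 2 row reads "Grade 2 (>3.0 and $\leq 5.0 \times$ ULN) without total bilirubin elevation to $>2.0 \times$ ULN", and its action is to keep the dose level and monitor liver tests. The Grade 3 row reads "Grade 3 (>5.0 and $\leq 20.0 \times$ ULN) without total bilirubin elevation to $>2.0 \times$ ULN", and its action is to omit drug and then reduce one level. The Grade 4 row (>20.0 × ULN) has the same bilirubin condition and action as Grade 3.
- **AST or ALT with concurrent bilirubin.** AST or ALT >3.0 × ULN with total bilirubin >2.0 × ULN means permanent discontinuation, "in the absence of cholestasis or hemolysis".

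Section 6.3.4.2 adds monitoring: "In case of any occurrence of ALT/AST/total bilirubin increase to grade 2 the LFTs must be monitored weekly". Its potential-DILI criterion for patients with normal baseline values is "AST or ALT $> 3.0 \times$ ULN combined with TBIL $> 2.0 \times$ ULN".

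**The concern.** A dose-modification table should not become more permissive as the liver picture worsens. Here the bilirubin Grade 2 row drops out once both enzymes exceed 3.0 × ULN, but the rule that takes over above that enzyme level starts only at bilirubin >2.0 × ULN. Between 1.5 and 2.0 × ULN the patient falls to a row written for enzyme elevation, which tells the site to continue.

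Hepatotoxicity is a listed adverse event of special interest (Section 8.2). The state is reachable under the entry criteria. Section 5.2, criterion 13, admits patients with liver metastases at AST/ALT up to 5 × ULN, and bilirubin up to 1.5 × ULN is allowed. A patient who enters with both enzymes above 3.0 is in the affected band as soon as bilirubin passes 1.5. At stake is continued dosing in a state worse than one for which the same table requires a hold.

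**Working it through.** There is no sample size or error rate to reproduce. The check is to apply the rows of Table 6-3 as rules, in × ULN, for a patient without Gilbert syndrome.

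**Inputs (all from Table 6-3)**
- B2: bilirubin >1.5 and ≤3.0, with AST or ALT ≤3.0 → omit.
- E1: AST/ALT >1 and ≤3.0 → keep dose.
- E2: AST/ALT >3.0 and ≤5.0, bilirubin not >2.0 → keep dose.
- E3/E4: AST/ALT >5.0, bilirubin not >2.0 → omit, then reduce one level.
- C: AST or ALT >3.0 and bilirubin >2.0, no cholestasis or hemolysis → permanent discontinuation.

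**Result at bilirubin 1.6, 1.8 and 2.0 (the same at all three)**

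| AST = ALT | Matching rows | Action |
|---|---|---|
| 0.9 | B2 | omit |
| 2.5 | B2, E1 | omit (bilirubin Grade 2 is the worse toxicity) |
| 4 | E2 only | keep dose |
| 5 | E2 only | keep dose |
| 6 | E3 | omit, then reduce |
| 21 | E4 | omit, then reduce |

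As the enzymes rise at fixed bilirubin, the action runs hold, continue, hold. Because both enzymes exceed 3.0 in the middle rows, the result is the same whether the enzyme condition in B2 is read as either enzyme or both.

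**Does another written rule change the middle rows?**
- Row C does not apply, because it needs bilirubin >2.0. The Section 6.3.4.2 criteria for potential DILI do not apply for the same reason.
- The general rules in Section 6.3.1 are headed as covering toxicities not listed in Table 6-3. Even if applied, they encourage continuing at the current dose for tolerable Grade 2 toxicity.
- Basing changes on the worst preceding toxicity does not settle it. Both abnormalities are Grade 2, and the bilirubin row carries an explicit enzyme condition.
- The table's bilirubin footnote begins "If Grade 3 or 4 hyperbilirubinemia is due to the indirect (non-conjugated) component only, and hemolysis as the etiology has been ruled out", so it starts at bilirubin >3.0.
- For Grade 2 abnormalities Section 6.3.4.2 requires weekly testing, not a hold.

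**Test of the fix**
- At bilirubin 1.8 with the two changes below, enzymes of 0.9, 2.5, 4 and 5 all give omit, and 6 and 21 give omit then reduce. The order is restored.
- Simply changing 2.0 to 1.5 in E2 would not be enough. Take an eligible Gilbert patient with total bilirubin 1.8, normal direct bilirubin and AST = ALT 4. E2 would no longer apply because total bilirubin is above 1.5. B2 would not apply because direct bilirubin is normal. C would not apply because total bilirubin is not above 2.0. The patient would have no row. With the direct-bilirubin provision, E2 still applies and the dose is kept, as now.

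**The case against.** The strongest reply is that the band is narrow and well guarded. Bilirubin and enzymes are all Grade 2. Liver tests are at least weekly. Section 6.3.2 permits interruptions. Section 6.3.1 allows a safety-driven variance, without prior sponsor discussion if urgent, and Section 12.1 expects immediate action for patient safety. Above 2.0 × ULN, without cholestasis or hemolysis, drug is stopped for good. All of this stands and limits exposure. None of it changes the instruction in the row: these provisions let an investigator depart from the table or catch the patient later. Tolerance of AST/ALT 3–5 × ULN makes sense for patients with liver metastases, but it does not explain continuing at a bilirubin that requires a hold even with normal enzymes.

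A reader might infer more than the documents support:
- **That the number affected can be bounded from Table 1-1.** It cannot. That table counts reported adverse events, and under Sections 8.1.1 and 8.1.2.1 a laboratory value is an adverse event only if it is clinically significant, causes signs or symptoms, needs therapy or changes study drug. A bilirubin of 1.8 × ULN under a continue instruction need not appear.
- **That the step from continuing (bilirubin 1.9, both enzymes 4.0) to permanent discontinuation (2.1) is itself an error.** That is a design choice. It follows the protocol's own potential-DILI threshold for patients with normal baseline values.
- **That the hepatic rules fail more widely.** Section 6.3.4.2 conditions its stop as follows: "In the absence of cholestasis, these patients should be immediately discontinued from study drug treatment". The table's concurrent row also excludes hemolysis. The bilirubin rows are also unclear when only one enzyme is ≤3.0. These points merit optional clarification, but the finding does not rest on them.

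**Conclusion.** The inconsistency is real as written. It is confined to total bilirubin >1.5–2.0 × ULN with AST and ALT both >3.0–5.0 × ULN, in patients without Gilbert syndrome, with the table followed literally. In that band Table 6-3 gives a less cautious action than it gives at the same bilirubin with lower enzymes, and no other written rule overrides it.

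Its frequency is not given in the documents. Nothing in them shows that any patient was in this state or was harmed, and no endpoint or analysis is shown to be affected. The case for correcting it is that a safety instruction is in the wrong order and can be put right by editing a table.

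**What to change.** Amend Table 6-3 in two places.

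1. Limit the AST/ALT Grade 2 continue row to total bilirubin ≤1.5 × ULN. For patients with Gilbert syndrome, limit it instead to direct bilirubin ≤1.5 × ULN and keep the present total bilirubin limit of 2.0 × ULN, so that none of them loses a row.
2. Apply the bilirubin Grade 2 hold at >1.5–2.0 × ULN (direct bilirubin in Gilbert syndrome) whatever AST/ALT is, released when bilirubin is ≤1.5 × ULN. Where an AST/ALT Grade 3–4 row also applies, its stricter action prevails.

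The change uses tests already collected. The cost is a few more dose holds; the documents do not allow a count. Because release from the Grade 2 hold depends on bilirubin, a patient with liver metastases and baseline AST/ALT of >3.0–5.0 × ULN is not kept off drug by the baseline enzymes.

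The SAP (Section 2) records early termination by the sponsor, with survival follow-up closed on August 4, 2016. The practical benefit is therefore limited to any patients still being dosed and to reuse of this table in other ceritinib protocols.

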 - Patients with plasmacytoma must have a definite increase in the size; a definite increase is defined as a 50% (and at least 1 cm) increase as measured serially by the sum of the products of the cross-diameters of the measurable lesion
 - d. **Leukemia only:** Relapsed/refractory leukemia for which no standard therapy options are anticipated to result in a durable remission:

- Acute myelogenous leukemia (AML) by World Health Organization (WHO) classification or acute lymphoblastic leukemia (ALL) relapsed or refractory to standard chemotherapy; unsuitable for standard chemotherapy or unwilling to undergo standard chemotherapy. Philadelphia chromosome (Ph) positive ALL eligible if failed prior tyrosine-kinase inhibitor therapy.
 - Age > 60 years with AML not candidates for or have refused standard chemotherapy, excluding patients with acute promyelocytic leukemia (APL) or with favorable cytogenetic abnormalities [inv16, t(8;21)]
 - For patients with Chronic Myeloid Leukemia (CML) only accelerated and blast phase CML will be allowed
9. Patient has an Eastern Cooperative Oncology Group (ECOG) performance status ≤ 1 ([Appendix M](#))
 10. Patient has a life expectancy of at least 16 weeks
 11. Patients must have adequate bone marrow as described below:
 - a. Absolute Neutrophil Count (ANC) $\geq 1.5 \times 10^9/L$ (not applicable for leukemia patients)
 - b. Platelets (PLT) $\geq 75 \times 10^9/L$ (no platelet transfusion within past 14 days) (not applicable for leukemia patients)
 - c. Hemoglobin (Hgb) $\geq 8 \text{ g/dl}$ (not applicable for leukemia patients)
 12. Patient must meet the following laboratory values at the screening visit:
 - International Normalized Ratio (INR) ≤ 1.5
 - Serum amylase $\leq 2 \times \text{ULN}$
 - Serum lipase $\leq \text{ULN}$
 - Alkaline phosphatase (ALP) $\leq 5.0 \times \text{ULN}$
 - Fasting plasma glucose $\leq 175 \text{ mg/dL} (\leq 9.8 \text{ mmol/L})$
 13. All patients must have adequate organ function defined as described below:
 - a. Potassium, calcium (corrected for serum albumin), phosphorus and magnesium within normal limits (WNL). Supplementation is allowed to meet eligibility requirements
 - b. Serum creatinine $< 1.5 \text{ mg/dl}$ and/or calculated creatinine clearance (using Cockcroft-Gault formula) $\geq 30 \text{ mL/min}$

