6.3 Dose modifications

6.3.1 Dose modification and dose delay

For patients who do not tolerate the protocol-specified dosing schedule despite maximal medical support (e.g. loperamide, ondasetron), dose adjustments are permitted in order to

allow the patient to continue the study treatment. Any changes in ceritinib administration must be recorded on the Dosage Administration Record eCRF.

Ceritinib dose modification guidelines are described in [Section 6.3.2](#). Any planned variance from these guidelines in the view of the patient safety must be previously discussed with the sponsor unless there is an urgent need for action.

All dose modifications, interruptions or discontinuations must be based on the worst preceding toxicity as graded by the NCI Clinical Toxicity Criteria for adverse events (NCI-CTCAE version 4.03). Once a dose has been reduced during a treatment cycle, re-escalation will not be permitted during any subsequent cycle.

General guidelines for dose modifications for toxicities other than those listed in [Table 6-3](#):

For grade 1 and tolerable grade 2 treatment-related toxicities, patients are encouraged to continue at the current dose of study treatment. For intolerable grade 2 treatment-related toxicities, dosing should be interrupted until resolution to grade 1 or lower followed by dose reduction to the next dose level.

For grade 3 or grade 4 treatment-related toxicity that is not considered by the investigator to be life-threatening, patients should interrupt study treatment until resolution to grade 1 or lower; then study treatment may continue following a dose reduction to the next dose level, if, in the opinion of the Investigator, the patient continues to experience clinical benefit. For any grade 3 or 4 treatment-related toxicity that is considered by the investigator to be life-threatening, permanently discontinue study treatment.

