6.3.3 Criteria for interruption and re-initiation of ceritinib treatment

If the administration of ceritinib is temporarily interrupted for reasons other than toxicity then treatment with ceritinib will be resumed at the same dose.

If treatment with ceritinib is withheld due to toxicity, scheduled visits and all assessments will continue to be performed (with the exception of the dosing of the withheld study drug), as described in [Table 7-1](#).

If treatment with ceritinib is withheld for more than 21 consecutive days (counting from the first day when a dose was missed) due to treatment-related toxicity, then ceritinib should be permanently discontinued except in cases where the investigator believes the patient continues to derive clinical benefit. In such cases, treatment with ceritinib may be resumed at a lower dose.

Patients whose treatment is temporarily interrupted or permanently discontinued due to an AE or abnormal laboratory value must be followed until resolution or stabilization of the event, whichever comes first, including all study assessments appropriate to monitor the event. Detailed guidelines for follow-up of study drug related AEs or abnormal laboratory values must be followed as described in [Section 6.3.4](#).

All patients will be followed for safety until 30 days after the last dose of ceritinib. Patients ongoing at the time of data cutoff for the CSR for this study may continue to receive treatment in the current study until:

- All patients have died or discontinued from the study
- Another clinical study becomes available that can continue to provide ceritinib in this patient population and all patients ongoing are eligible to be transferred to that clinical study
- At the end of the study, every effort will be made to continue provision of study treatment outside this study through an alternative setting to patients who in the opinion of the Investigator are still deriving clinical benefit.

The final analysis will occur at the end of the study. All available data from all patients up to this cut-off date will be analyzed and summarized in a final CSR.

Table 6-3 Ceritinib related toxicity management guidelines

Worst toxicity (CTCAE 4.03 Grade)*	Dose Modifications for ceritinib
HEMATOLOGICAL	
Neutropenia (ANC)	
Grade 1 (ANC < LLN - $1.5 \times 10^9/L$) Grade 2 (ANC < 1.5 and $\geq 1.0 \times 10^9/L$) Grade 3 (ANC < 1.0 and $\geq 0.5 \times 10^9/L$)	Maintain dose level

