6.3.4.3 Guidelines for the follow-up of laboratory renal abnormalities

In case of any occurrence of serum creatinine results of grade 2, tests must be performed weekly (or more frequently if clinically indicated) until the event resolves to \leq grade 1. Subsequent monitoring must be performed every 4 weeks.

In case of any occurrence of serum creatinine \geq grade 3, tests must be performed twice weekly (or more frequently if clinically indicated) until the event resolves to \leq grade 1. Subsequent monitoring must be performed every 4 weeks. See [Table 6-4](#).

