Investigations (renal)	Serum creatinine Grade 2: Test weekly (or more frequent) until Grade 1 Thereafter, test every cycle (4 weeks) Serum creatinine \geq Grade 3: Test twice weekly (or more frequent) until \leq Grade 1 Thereafter, test every cycle (4 weeks)
Investigations (pancreatic)	Amylase/lipase \geq Grade 3: Test weekly (or more frequently) until \leq Grade 1. After resumption of dosing, continue to test weekly for one additional cycle (4 weeks). If no reoccurrence of \geq Grade 2 event, continue monitoring every cycle (4 weeks).

*Note: this table refers to the evaluation schedule only. Refer to [Table 6-3](#) for dose modifications required for applicable toxicities

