10.5.3.1.2 Laboratory abnormalities

All laboratory values will be converted into SI units and the severity grade will be calculated using appropriate common terminology criteria (CTCAE v4.03).

A severity grade of 0 will be assigned when the value is within normal limits. For lab parameters for which severity grades are determined both through normal limits and absolute cut-offs, in the unlikely case when a local laboratory normal range overlaps into the higher (i.e. non-zero) CTCAE grade, the laboratory value will still be taken as within normal limits and assigned a CTCAE grade of zero.

A listing of laboratory values will be provided by laboratory parameter, patient, and treatment arm. A separate listing will display notable laboratory abnormalities (i.e., newly occurring CTCAE grade 3 or 4 laboratory toxicities). Lab values collected later than 30 days after study treatment discontinuation will be flagged in the listings.

The following by-group summaries will be generated separately for hematology, and biochemistry parameters:

[figure not shown]
- shift tables using CTCAE grades to compare baseline to the worst on-treatment value
- for laboratory tests where CTCAE grades are not defined, shift tables using the low/normal/high/(low and high) classification to compare baseline to the worst on-treatment value.
- listing of all laboratory data with values flagged to show the corresponding CTCAE grades and the classifications relative to the laboratory normal ranges.

[figure not shown]

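### Table 6-3 prints two serum creatinine grade sets whose Grade 1 to 3 cut-offs conflict, and no text says which one governs dose holds, restart and monitoring

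*Protocol*

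**What the plan says.** The grade column of Table 6-3 is headed as CTCAE 4.03 grade. Under Renal, serum creatinine, the table gives two sets:

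| Grade | Labelled set | Set without its own heading | Action in both |
|---|---|---|---|
| 1 | >1 to ≤1.5 × baseline; >ULN to ≤1.5 × ULN | >ULN to <1.5 × ULN | Continue at same dose |
| 2 | >1.5 to ≤3.0 × baseline; >1.5 to ≤3.0 × ULN | ≥1.5 to ≤3.0 × ULN | Hold to Grade 1 or lower; same dose if that takes 7 days or less, otherwise one level down |
| 3 | >3.0 × baseline; >3.0 to ≤6.0 × ULN | >3.0 to ≤6.0 × ULN | Hold to Grade 1 or lower, then one level down |
| 4 | >6.0 × ULN | >6.0 × ULN | Stop permanently |

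In the labelled Grade 2 row a bare semicolon joins the two criteria: "baseline; >1.5 and". The matching row of the other set is "Grade 2 (≥1.5 and ≤3.0 x ULN", with no baseline term.

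Other provisions use the grade number without restating cut-offs:

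- Section 6.3.1: dose changes "must be based on the worst preceding toxicity as graded by the NCI Clinical Toxicity Criteria for adverse events", version 4.03.
- Section 6.3.4.3: "In case of any occurrence of serum creatinine results of grade 2, tests must be performed weekly"; Grade 3 or higher is tested twice weekly. Table 6-4 repeats this: "Serum creatinine Grade 2: Test weekly (or more frequent) until Grade 1".
- Section 6.3.2: a reduced dose is never raised again.
- Section 10.5.3.1.2, repeated in SAP Section 7.4, gives a rule for the analysis: "A severity grade of 0 will be assigned when the value is within normal limits". No text says whether it also applies to dosing.

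**The concern.** A site reading the table has two sets of thresholds for the same laboratory value. Which one it follows decides four things: whether drug is held, the level at which it restarts, whether it restarts at the same dose or irreversibly one level lower, and how often creatinine is tested. Two sites could treat identical values differently and both be able to point to the table. The affected outputs are the consistency of renal dose handling and the dose-change and dose-intensity summaries in SAP Section 5.1.

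**Working it through.** The plan gives no figure to reproduce, so the check applies both sets to the same values. ULN is not in the documents; 1.2 mg/dL is assumed, with a range of 1.0 to 1.3. The baselines are also illustrative. The semicolon is undefined, so two readings are tried.

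**Reading 1: 'or, whichever gives the worse grade'.** The labelled set requires a hold above 1.5 × baseline whenever baseline is below ULN. The other set requires a hold from 1.5 × ULN. Counting only values above ULN, to leave aside the unsettled Grade 0 question, the hold conflict runs from above max(ULN, 1.5 × baseline) to below 1.5 × ULN (mg/dL):

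| Baseline | ULN 1.0 | ULN 1.2 | ULN 1.3 |
|---|---|---|---|
| 0.6 | 1.00–1.50 | 1.20–1.80 | 1.30–1.95 |
| 0.8 | 1.20–1.50 | 1.20–1.80 | 1.30–1.95 |
| 1.0 | none (baseline equals ULN) | 1.50–1.80 | 1.50–1.95 |

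- *Hold.* Baseline 0.8, value 1.4: 1.4/0.8 = 1.75, Grade 2 (hold, weekly tests). Against ULN, 1.4/1.2 = 1.17 (1.40 at ULN 1.0, 1.08 at ULN 1.3), Grade 1 (continue). The conflict holds over the whole ULN range.
- *Restart.* Baseline 0.8, value 2.0: Grade 2 in both sets (2.0/0.8 = 2.50; 2.0/1.2 = 1.67, range 1.54 to 2.00). Restart is at 1.5 × 0.8 = 1.20 or lower in one set and below 1.80 (1.50 to 1.95) in the other. At ULN 1.3 the labelled level becomes 1.30 if in-range values count as Grade 0.
- *Grade 3 versus lower.* Values above 3 × baseline but not above 3 × ULN. Baseline 0.6, value 1.9: 1.9/0.6 = 3.17, Grade 3. Against ULN, 1.9/1.2 = 1.58 and 1.9/1.0 = 1.90 give Grade 2, but 1.9/1.3 = 1.46 gives Grade 1. One set forces a reduction and twice-weekly tests. The other allows the same dose after a short hold or, at ULN 1.3, no hold.
- With baseline at or above ULN, the sets differ only at exactly 1.5 × ULN (Grade 1 versus Grade 2).

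**Reading 2: baseline multiples apply only when baseline is above ULN.** Such patients can enter, because inclusion criterion 13b accepts creatinine below 1.5 mg/dL "and/or calculated creatinine clearance (using Cockcroft-Gault formula") of at least 30 mL/min. For baseline at or below ULN the sets then agree except at exactly 1.5 × ULN. For baseline above ULN they conflict in two ranges, shown for baseline 1.4:

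- From 1.5 × ULN to 1.5 × baseline: 1.80 to 2.10 (lower end 1.50 to 1.95). A value of 2.0 gives 2.0/1.4 = 1.43, Grade 1 (continue), against 2.0/1.2 = 1.67 (1.54 to 2.00), Grade 2 (hold).
- Above 3 × ULN to 3 × baseline: 3.60 to 4.20 (lower end 3.00 to 3.90). These values are Grade 2 against Grade 3.

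Neither reading removes the conflict; it moves from patients with baseline below ULN to those above it.

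**The case against.** **The second set may be deleted text.** The amendment sections say deletions appear in strike-through red, and plain text does not carry that formatting. Amendment 1 logs an update to the renal creatinine rows, and an older ULN-only set beside a newer one is what a leftover would look like. Section 1.2.3.3 also carries two near-identical phototoxicity paragraphs, so duplicates do survive. This cannot be fully excluded and should be checked against the formatted protocol, but it is unlikely. The renal change belongs to Amendment 1, while the only Table 6-3 change logged for Amendment 2 concerns QTc. Other logged deletions (the old contraception combinations, the BIRC wording in Section 6.4.2.4) are gone from the body. A leftover that is still printed also still instructs sites.

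**The block may not be creatinine.** It follows a repeated table header and has no row label. That stands as a caveat: the attribution rests on its position between the serum creatinine rows and the gastrointestinal heading.

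**CTCAE 4.03 is the named authority.** It is, but both sets sit under that same column header and the documents do not reproduce its creatinine grades, so the reference does not choose between them.

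**The consequences are small.** Largely true. The actions and the Grade 4 cut-off match, laboratory tables are graded by CTCAE v4.03 under SAP Section 7.4 rather than by Table 6-3, and SAP Section 2 records early termination. This limits the severity but does not resolve the conflict.

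**Conclusion.** The table is wrong as written: at the same creatinine value one set says continue and the other says hold, and no provision ranks them. Severity is minor. The existence and location of the conflict follow from the printed cut-offs; the mg/dL bands rest on the assumed ULN, the illustrative baselines and the reading of the semicolon.

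A reader might infer three stronger things that the documents do not support.

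- *That about 15% of patients are affected*, from Table 1-1 (39/255 = 15.3% with creatinine increased, none at Grade 3/4). Those are reported adverse events by preferred term, not laboratory values set against either group of cut-offs. Under Section 8.1.1 of this protocol a laboratory abnormality is an adverse event only if it is clinically significant, causes symptoms, or needs therapy or a change of drug. The number of patients in the conflicting ranges is unknown.
- *That longer holds would force patients off drug and so reach the clinical benefit rate.* After more than 21 days, drug "should be permanently discontinued except in cases where the investigator believes the patient continues to derive clinical benefit", and it may then resume at a lower dose. The Grade 4 stopping rule is identical in both sets. The primary endpoint is unaffected.
- *That the second set is a known leftover of Amendment 1.* The log says only that the renal rows were updated; why the second set is there is not stated.

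**What to change.** Keep one creatinine set, presumptively the labelled one, and delete the four ULN-only rows once the sponsor's clinical team confirms. Add a note that:

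- the semicolon means 'or, whichever gives the worse grade';
- values within normal limits are, or are not, Grade 0 for dosing;
- the same cut-offs define recovery to Grade 1 or lower and the grades used in Section 6.3.4.3 and Table 6-4.

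The cost is four rows and one note, by amendment or site letter, with no added patients or procedures. Because the study was terminated early, the remaining reach is any patient still on drug, plus one sentence in the study report saying which set drove creatinine-related dose changes.
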